9.3.7 Immunogenicity Analyses

All immunogenicity listings and analyses will be based on the safety analysis set as described in [Section 9.2](#).

Antibody response will be listed by subject as negative or positive with a specific titer.

Tables summarizing the frequency of the occurrence of ADAs by ZW25 dose and by time point with overall summary per ZW25 dose will be produced. Titers for confirmed positive ADA will be summarized. The time of onset of immunogenicity, duration, and number of resolved ADA cases will be summarized. Summary statistics for domain specificity and neutralizing potential will be included, if available.

Effect of immunogenicity on PK and specifically clearance of ZW25 will be explored.

Further details of the immunogenicity analyses will be described in the SAP.

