In non-GLP pharmacokinetic (PK) and GLP TK studies, ZW25 serum exposure increased with dose (5 mg/kg through 150 mg/kg IV) in cynomolgus monkeys. ZW25 was mostly distributed to the serum compartment and was cleared slowly from the serum. Mean half-life of ZW25 after either a single dose or repeat doses ranged from 74.3 to 215 hours (2.73 to 8.95 days) and was similar to the reported half-life (3 to 14 days) of trastuzumab from repeat-dose studies in rhesus and cynomolgus monkeys (EMEA 2005). Cohorts from all dosing levels of the GLP toxicology study of ZW25 were screened for antidrug antibodies (ADA). Only 2 of the 292 samples tested were confirmed positive; however, the majority of ZW25-treated animals had serum concentrations that exceeded the specific drug tolerance level of the assay. Thus, ADA may be present but undetectable due to high drug concentrations.

The GLP toxicology study evaluated the toxicity and toxicokinetics (TK) of weekly ZW25 at doses of 5, 50, and 150 mg/kg for 8 and 13 weeks. ZW25 was well tolerated and no adverse effects were observed at weekly doses up to 150 mg/kg IV for up to 13 weeks.

The nonclinical program supported evaluation of ZW25 as an IV infusion in the clinic. Therefore, a first-in-human clinical study was initiated in September 2016. This ongoing, multi-part, Phase 1 study (ZWI-ZW25-101) is evaluating the safety, pharmacokinetics (PK), immunogenicity, and anti-tumor activity of ZW25 as a single agent and in combination with selected chemotherapy agents in subjects with locally advanced (unresectable) and/or metastatic HER2-expressing tumors.

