6.6 Efficacy Follow-up (Every 8 weeks)

Subjects who have discontinued all study treatment on either part of the study for reasons other than progression or start of subsequent anticancer therapy will continue in follow-up with disease assessments approximately every 8 weeks after the previous scan until disease progression or start of subsequent anticancer therapy. The efficacy follow-up will include the following assessments:

- Disease assessment per RECIST 1.1 (CT/MRI scans, and breast cancer serum tumor markers [if being monitored])
- Bone scan (scintigraphy): For subjects with new lesions identified by post-baseline bone scintigraphy, targeted assessment by X ray, CT scan with bone windows, or MRI will be performed to confirm findings.
- Brain scan (MRI): After screening, brain scans will be required per protocol only for subjects with findings on the screening brain scan; for subjects without findings on the screening brain scan, subsequent brain scans will be done per institutional standard of care.
- ADA sample (only if a subject had an ongoing anti-ZW25 ADA present at the safety follow-up visit): These will be discontinued after the resolution of ADA.

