7.5 Immunogenicity Assessments

Blood samples to test for antibodies to ZW25 will be obtained at selected time points specified in the assessment schedule ([Appendix A](#)). Blood samples for ADAs will be taken before the start of the ZW25 infusion. All ADA blood sample collection time points during the first 2 treatment cycles coincide with a pre-dose PK sample time point. If a subject terminates early from the clinical trial, all efforts will be made to collect blood samples to test for antibodies to ZW25 unless consent has been withdrawn. Additional samples may be drawn in the event of an infusion reaction.

The immunogenicity testing will be performed in 3 steps as follows: screening assay (Tier 1), confirmation assay (Tier 2), and titration (Tier 3). Only samples positive in the screening assay will be tested in confirmation and further titrated to determine the titer of ADA.

For any samples that are confirmed positive for anti-ZW25 antibody, there may be additional testing done to characterize domain specificity and possibly the anti-ZW25 antibody potential for neutralizing activity on ZW25.

Additional sample handling, processing, storage, labeling, and shipping instructions will be provided to the site in the Laboratory Manual.

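### ADA results have only two states, so a sample masked by circulating ZW25 would count as negative and ADA frequency, a secondary endpoint, could be understated

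*Combined protocol and SAP*

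**What the plan says.** Section 9.3.7 sets the reporting format: "Antibody response will be listed by subject as negative or positive with a specific titer". It then tabulates ADA frequency by ZW25 dose and time point with an overall summary per dose, and summarises onset, duration and the number of resolved cases. It adds that "Effect of immunogenicity on PK and specifically clearance of ZW25 will be explored", and leaves further detail to the SAP. Sections 2.1 and 2.2 make ADA frequency, duration and onset secondary endpoints in both parts.

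Section 7.5 describes a three-tier assay: "Only samples positive in the screening assay will be tested in confirmation and further titrated to determine the titer of ADA". It gives no drug-tolerance limit and no step that looks at the ZW25 concentration in a screen-negative sample.

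Section 1.4 describes the GLP toxicology study in monkeys. "Only 2 of the 292 samples tested were confirmed positive", but "the majority of ZW25-treated animals had serum concentrations that exceeded the specific drug tolerance level of the assay". The protocol draws the inference itself: "Thus, ADA may be present but undetectable due to high drug concentrations".

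**The concern.** A negative screen is informative only if the drug in the sample is low enough for the assay to see antibody. Above that level the sample says nothing about ADA, yet under two states it joins the negatives. Three outputs would be exposed.

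- **Frequency.** Hidden positives leave the numerator but stay in the denominator, so the reported rate would be a lower bound presented as an estimate.
- **Onset and resolution.** ADA seen early and then hidden as drug accumulates would look resolved. ADA seen only after washout would be given a late onset.
- **Clearance.** Subjects who clear ZW25 quickly have lower troughs, so their ADA is easier to detect. Detected ADA could then go with fast clearance through selection alone.

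A related gap is that the overall summary in section 9.3.7 does not separate ADA already present at the Cycle 1 Day 1 predose sample from ADA that develops on treatment.

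**Working it through.** The plan states no expected ADA rate or precision, so there is no design figure to reproduce.

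**1. Can a drug level be attached to each ADA sample?** (Sections 6.3 to 6.6 and 7.5, Appendices A to C, with sampling stopped after Cycle 4 under the February 2023 memorandum.)

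| ADA sample | ZW25 measured at the same time |
|---|---|
| Cycle 1 Day 1 predose | Yes (before any ZW25) |
| Cycle 1 Day 15, Cycle 2 Days 1 and 15, Cycle 4 Day 1, all predose | Yes |
| End of treatment | Only if under 6 months of treatment |
| About 30 days after the last dose of any study drug | None scheduled |
| Efficacy follow-up (only if ADA was present at the 30-day visit) | None scheduled |

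On-treatment samples can therefore be classified with existing data. The 30-day sample, where the drug has had longest to wash out, cannot. A negative there also ends ADA sampling.

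**2. Frequency.** Observed = true × (1 − m), where m is the share of positives masked. With m = 0.5, true rates of 5%, 10% and 20% become 2.5%, 5% and 10%. With m = 0.9 they become 0.5%, 1% and 2%. With m = 0 nothing changes. The documents do not give m.

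**3. Is masking likely at trough?** The only half-lives are the monkey means in section 1.4, 74.3 to 215 hours (74.3/24 = 3.10 days; 215/24 = 8.96 days). Residual fraction = 2^(−t/half-life).

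- At 14 days: 0.0435 to 0.3385.
- At 30 days: 0.0012 to 0.0982.
- Steady-state trough relative to first trough, 1/(1 − fraction at 14 days): 1.05 to 1.51.

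To put this on a concentration scale, assume 20 mg/kg distributed in 50 mL/kg, a rise of 400 µg/mL per dose (the volume is an assumption). The steady-state trough is 400 × f/(1 − f), with f the 14-day fraction:

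- 74.3 h: 400 × 0.0435/0.9565 ≈ 18 µg/mL.
- 215 h: 400 × 0.3385/0.6615 ≈ 205 µg/mL.

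Against an assumed tolerance of 25 to 100 µg/mL, the typical trough lies below the whole range at one end and above it at the other. The documents cannot settle the question.

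**4. Direction of any clearance distortion.** This was a simulation of 1,000,000 subjects per scenario. All inputs are assumptions: lognormal clearance with CV 30%, median half-life 6 days, every-2-week steady-state trough, 20% sample noise, true ADA 10%. Entries are geometric mean clearance ratios, ADA-positive over ADA-negative.

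| True ratio | Masking | Share masked | Two states | Inconclusives removed |
|---|---|---|---|---|
| 1.00 | follows own drug level | 50% | 1.26 | 1.00 |
| 1.00 | follows own drug level | 80% | 1.50 | 1.00 |
| 1.00 | unrelated to drug level | 50% or 80% | 1.00 | 1.00 |
| 1.25 | follows own drug level | 50% | 1.57 | 1.08 |
| 1.25 | follows own drug level | 80% | 1.85 | 1.05 |
| 1.25 | unrelated to drug level | 50% | 1.23 | 1.25 |
| 1.25 | unrelated to drug level | 80% | 1.22 | 1.25 |

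With true ADA at 30% the pattern is the same. The table shows direction only. It does not forecast this trial.

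**5. How many subjects have clearance?** Section 9.3.6 derives it after dose 1 from extensive sampling. Section 7.3 assigns that schedule to all of Part 1 and at least six subjects in Part 2. The planned minimum is 6 + 6 = 12, more if step-down cohorts open. At an assumed 10% ADA, 12 subjects contain 12 × 0.10 = 1.2 positives.

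**The case against.** The strongest reply is that nothing shows masking in this trial. Section 1.4 concerns the assay used in monkeys dosed at 5, 50 and 150 mg/kg weekly. A reader might infer that ADA frequency here is understated, but without the clinical assay's tolerance or a human concentration that is not established. This stands, and the point is conditional.

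A reader might also infer that the clearance analysis is bound to show a false effect. It is not. That direction needs masking to follow each subject's own drug level; masking unrelated to it leaves a null ratio at 1.00 and dilutes a real one. The analysis is also only exploratory, with no grouping or model specified, and may rest on about a dozen subjects.

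Third, section 9.3 calls itself a summary and sends detail to a SAP, and no separate SAP text is available to check. The SAP could add the missing category. That lowers the severity but does not remove the point, because the two-state wording and the stop at a negative screen are what the protocol now prescribes.

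Fourth, there are safeguards: predose sampling, paired PK in Cycles 1, 2 and 4, and a washout sample. Subjects who stop ZW25 but continue the other drugs have a longer ZW25 washout by the 30-day visit. These reduce the risk, but nothing in section 9.3.7 uses the paired PK to qualify a negative.

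On baseline ADA, the by-time-point table would show Cycle 1 Day 1 positives. A reader might infer that earlier trastuzumab and pertuzumab leave antibodies that cross-react with ZW25. Section 1.4 says only that the epitopes are shared, which does not establish that. The separation is worth making for clarity, not because cross-reactivity is shown.

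**Conclusion.** The point holds as a conditional weakness in how ADA results are classified. If clinical ZW25 concentrations exceed the clinical assay's tolerance, the rule as written scores uninformative samples as negative. Any error in frequency would then be downward, onset and resolution could be misdated, and the clearance comparison could be exaggerated or diluted depending on what drives the masking.

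The size is unknown and could be nil. It depends on two quantities the documents do not give: the validated tolerance and human trough concentrations. If the tolerance comfortably exceeds the observed troughs, stating so closes the matter. PFS6 and the other tumour endpoints are not affected.

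**What to change.** In section 9.3.7 and the SAP:

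1. State the validated drug tolerance of the clinical ADA assay.
2. Classify each sample as positive, negative (ZW25 at or below tolerance) or inconclusive (screen-negative with ZW25 above it). Use the paired predose PK samples and the end-of-treatment PK sample where one is taken. Flag negatives with no paired PK, such as those at the 30-day visit, as unverified.
3. Report ADA frequency twice: with inconclusive samples counted as negative, and with them excluded.
4. Report treatment-emergent ADA separately from ADA present at the Cycle 1 Day 1 predose sample.
5. In the exploratory clearance analysis, do not count inconclusive subjects as ADA-negative. Show results with and without them and interpret both with drug level in view. Removing them is not a complete cure: restricting to low-drug samples took a true ratio of 1.25 to 1.08 in the check above.

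The cost is wording and some extra tables built on data already collected. Fewer subjects can be called ADA-negative, and an already small clearance comparison becomes smaller.

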9.3.8 Biomarker Analyses

Potential biomarkers such as circulating tumor DNA (ctDNA), Prosigna (formerly called the PAM50 test), and HER2 ECD (but not limited to) will be summarized using descriptive statistics (i.e., n, arithmetic mean, geometric mean, median, standard deviation, range, coefficient of variance). Details will be described separately in the SAP.

9.3.9 Safety Analyses

All analyses of safety will be conducted on the safety analysis set unless otherwise specified. For Part 1 of the study, safety will be summarized separately by dose cohort. For Part 2 of the study, subjects treated at the RD in Part 1 will be included in all Part 2 analyses of safety.

9.3.9.1 Extent of Exposure

The frequency of dose reductions and discontinuations of ZW25, palbociclib, and fulvestrant will be summarized using counts and percentages. In addition, duration of exposure and total cumulative dose of ZW25, palbociclib, and fulvestrant as well as the total number of treatment cycles received will be summarized descriptively.

9.3.9.2 Dose-limiting Toxicities (DLTs)

The frequency of DLTs (as defined in [Section 3.1.2](#)) and the corresponding exact binomial 95% CI will be calculated for each dose cohort for Part 1 of the study only. This will be computed for the DLT Evaluable Set.

9.3.9.3 Adverse Events

An AE is defined as any untoward medical occurrence in a clinical study subject administered a medicinal product which does not necessarily have a causal relationship with this treatment. All AEs will be coded by the Sponsor to standard “preferred terms” and system organ classifications (SOC) using MedDRA. Severity will be graded by study investigators using ([NCI CTCAE](#)) v5.0.

The frequency of AEs will be summarized by preferred term and SOC using counts and percentages. In addition, treatment-related AEs and AEs which lead to premature discontinuation of study treatment will be summarized.

9.3.9.4 Deaths and Serious Adverse Events

The frequency of deaths will be summarized using counts and percentages. By-subject listings of deaths will also be produced.

The frequency of SAEs will be summarized by SOC and preferred term using counts and percentages. Treatment-related SAEs will also be summarized.

9.3.9.5 Clinical Laboratory Results

Summary statistics (mean, median, minimum, maximum, standard deviation) for actual value and change from baseline will be tabulated as appropriate for laboratory results.

Laboratory results will be graded using ([NCI CTCAE](#)) v5.0 and summarized by laboratory test and toxicity grade using counts and percentages.

9.3.9.6 Cardiac Function

The frequency of ECG abnormalities (e.g., heart rate, PR interval, QRS complex, and QTcF) will be summarized using counts and percentages. In addition, the percentage of subjects with LVEF <50% and \geq 50% and with an absolute decrease in LVEF \geq 10 percentage points will be summarized.

9.3.9.7 Vital Signs

Vital signs (blood pressure, heart rate, respiratory rate, and temperature) will be summarized using descriptive statistics (i.e., mean, median, standard deviation, and range).

9.3.9.8 ECOG Status

ECOG status will be summarized for each visit. Shifts from baseline to the best and worst post-baseline score may be tabulated.

9.3.9.9 ECG

ECG status (normal, abnormal clinically significant, or abnormal not clinically significant) may be summarized for each scheduled ECG and shifts from baseline may be tabulated.

9.3.10 Interim Analyses

A SMC will be responsible for monitoring subject safety (see Section 3.1). Cumulative safety reviews will be conducted per the SMC Guidelines and real-time review of related SAEs will be conducted. Also, interim data from the study may be presented at scientific meetings or in manuscripts.

10 INFORMED CONSENT, ETHICAL REVIEW, AND REGULATORY CONSIDERATIONS

10.1 Institutional Review Board (IRB) / Independent Ethics Committee (IEC)

Before initiation of the study at each study center, the protocol, the ICF, other written material given to the subjects, and any other relevant study documentation will be submitted to the appropriate IRB/IEC. Written approval or favorable opinion of the study and all relevant study information must be obtained before the study center can be initiated. Any necessary extensions or renewals of IRB/IEC approval/favorable opinion must be obtained for changes to the study such as amendments to the protocol, the ICF or other study documentation. The written approval of the IRB/IEC together with the approved ICF must be filed in the study files.

The investigator will report promptly to the IRB/IEC any new information that may adversely affect the safety of the subjects or the conduct of the study. The investigator will submit written summaries of the study status to the IRB/IEC as required. On completion of the study, the IRB/IEC will be notified that the study has ended.

10.2 Regulatory Authorities

Relevant study documentation will be submitted to the regulatory authorities of the participating countries, according to local/national requirements, for review and approval before the beginning of the study. On completion of the study, the regulatory authorities will be notified that the study has ended.

10.3 Ethical Conduct of the Study

The investigator(s) and all parties involved in this study should conduct the study in adherence to the ethical principles based on the Declaration of Helsinki, GCP, ICH guidelines, and the applicable national and local laws and regulatory requirements.

10.3.1 Informed Consent

The process of obtaining informed consent must be in accordance with applicable regulatory requirement(s) and must adhere to GCP.

The investigator is responsible for ensuring that no subject undergoes any study-related examination or activity before that subject has given written informed consent to participate in the study.

The investigator or designated personnel will inform the subject of the objectives, methods, anticipated benefits and potential risks and inconveniences of the study. The subject should be given every opportunity to ask for clarification of any points he or she does not understand and, if necessary, ask for more information. At the end of the interview, the subject will be given ample time to consider the study. Subjects will be required to sign and date the ICF. After signatures are obtained, the ICF will be kept and archived by the investigator in the investigator's study file. A signed and dated copy of the subject ICF will be provided to the subject or their authorized representative.

It should be emphasized that the subject may refuse to enter the study or to withdraw from the study at any time, without consequences for their further care or penalty or loss of benefits to which the subject is otherwise entitled. Subjects who refuse to give or who withdraw written informed consent should not be included or continue in the study.

If new information becomes available that may be relevant to the subject's willingness to continue participation in the study, a new ICF will be submitted to the IRB(s)/IEC(s) (and regulatory authorities, if required). The study subjects will be informed about this new information and reconsent will be obtained.

10.3.2 Subject Confidentiality

Monitors, auditors, and other authorized agents of the sponsor and/or its designee, the IRB(s)/IEC(s) approving this research, and the US FDA, as well as that of any other applicable agency(ies), will be granted direct access to the study subjects' original medical records for verification of clinical study procedures and/or data, without violating the confidentiality of the subjects to the extent permitted by the law and regulations. In any presentations of the results of this study or in publications, the subjects' identity will remain confidential.

All personal data collected and processed for the purposes of this study should be managed by the investigator and his/her staff with adequate precautions to ensure confidentiality of those data, and in accordance with the Health Insurance Portability and Accountability Act ([HIPAA 1996](#)) and applicable national and/or local laws and regulations on personal data protection.

10.4 Study Documentation and Records Retention

Essential documents are those documents that individually and collectively permit evaluation of the study and quality of the data produced. After completion of the study (end of study defined as the date of the last visit of the last subject), all documents and data relating to the study will be kept in an orderly manner by the investigator in a secure study file. This file will be available for inspection by the sponsor or its representatives. Essential documents should be retained for 2 years after the final marketing approval, for at least 2 years since the discontinuation of clinical development of the investigational product, or for the time period required by the applicable regulatory authorities. It is the responsibility of the sponsor to inform the study center when these documents no longer need to be retained. The investigator must contact the sponsor before

destroying any study-related documentation. In addition, all subject medical records and other source documentation will be kept for the maximum time permitted by the hospital, institution, or medical practice.

10.5 Clinical Trial Agreement

Payments by the sponsor to investigators and institutions conducting the study, requirements for investigators' insurance, the publication policy for clinical trial data, and other requirements are specified in the clinical trial agreement.

APPENDIX A: SCHEDULE OF EVENTS

Assessment	Screening Visit (≤ 28 days)	Cycle 1				Cycle 2			Additional 4-week cycles		Every 8 weeks (±7D)	EOT ^r (+14D)	Safety Follow-up (30 days post last dose) ^v (+7D)	Efficacy Follow-up (Q8W) ^v (+7D)	Survival Follow-up (Q3M) ^v (±7D)
		D1	D2	D5	D15 (±2D)	D1 (±2D)	D15 (±2D)	D28 (±7D)	D1 (±2D)	D15 (±2D)					
ZW25 ^a		X			X	X	X		X	X					
Palbociclib ^b		Taken orally QD with food from Day 1 through 21 (off treatment on Days 22 through 28) in a 28-day cycle													
Fulvestrant ^c		X			X	X			X						
LHRH analogue ^d		Dependent on the LHRH selected for administration by the investigator													
Informed consent	X														
Medical history	X														
Eligibility	X	X ⁱ													
Demographics	X														
New tumor biopsy or archived tissue	X ^l											X ^p			
Disease assessment (CT/MRI, & tumor markers) ^e	X							X			X	X ^s	X ^s	X ^s	
Bone scan (scintigraphy) ^e	X							X			X	X ^s	X ^s	X ^s	
Brain scan (MRI) ^e	X							X			X	X ^s	X ^s	X ^s	
Physical exam ^{f,j}	X	X			X	X	X		X	X		X	X		
ECOG PS ^{f,j}	X	X				X			X			X	X		
Vital signs ^k	X	X			X	X	X		X	X		X	X		
Hematology ^{f,j}	X	X			X	X	X		X	X		X	X		
Coagulation ^{f,j}	X	X													
Serum chemistry ^{f,i,y}	X	X			X	X	X		X	X		X	X		
Urinalysis	X														
Pregnancy test ^{f,j} (WOCBP only)	X	X				X			X			X	X		
12-lead ECG ^m	X	X							X			X	X		
Echo/MUGA ^{j,q}	X	First post-baseline scan at Cycle 3 Day 1 (approximately 8 weeks from Cycle 1 Day 1), Q12W thereafter													
Hepatitis B, C and HIV ^g	X														
ADA ^{j,z}		X			X	X	X		X ^o			X	X ^u	X ^w	
ctDNA ^j		X						X				X ⁿ	X ⁿ		
HER2 ECD ^j		X			X		X								
PK samples ^{h,z}		X ^{k,l}	X	X	X ^{k,l}	X ^{k,l}	X ^{k,l}		X ^{k,l}			X ^h			

Assessment	Screening Visit (≤ 28 days)	Cycle 1				Cycle 2			Additional 4-week cycles		Every 8 weeks	EOT ^r	Safety Follow-up (30 days post last dose) ^v	Efficacy Follow-up (Q8W) ^y	Survival Follow-up (Q3M) ^y	
		D1	D2	D5	D15 (±2D)	D1 (±2D)	D15 (±2D)	D28 (±7D)	D1 (±2D)	D15 (±2D)						(±7D)
AEs ^t		Study protocol-related AEs as well as any concomitant medications given for treatment of the AE, should be recorded from the time of informed consent. Otherwise, AEs and concomitant medications will be recorded from the start of dosing of any study drug on Cycle 1 Day through 30 days after last dose of study drug.														
Concomitant medications		Study drug (palbociclib only [other drugs administered at the clinic]) dispensing, collecting, and accountability will be conducted per Section 5.6														
Drug accountability																
Survival status follow-up																X ^x

ADA = anti-drug antibody; AE = adverse event; AESI = AE of special interest; CT = computed tomography; ctDNA: circulating tumor DNA; D = day; ECD = extracellular domain; ECG = electrocardiogram; Echo = echocardiogram; ECOG PS = Eastern Cooperative Oncology Group performance status; EOT = End of Treatment; HER2 = human epidermal growth factor receptor 2; HIV = human immunodeficiency virus; LHRH = luteinizing hormone releasing hormone; mos = months; MRI = magnetic resonance imaging; MUGA = multiple gated acquisition scan; PK = pharmacokinetics; q8w = once every 8 weeks; q3mos = once every 3 months; RECIST v1.1 = Response Evaluation Criteria in Solid Tumors version 1.1; WOCBP = women of childbearing potential only.

- ^a See [Section 5.2.2](#) for ZW25 dosing and administration. There must be a minimum of 10 days (±2 days) between doses. Day 15 doses not administered within 6 days after Day 15 must be skipped.
- ^b See [Section 5.3.2](#) for palbociclib dosing and administration.
- ^c See [Section 5.3.2](#) for fulvestrant dosing and administration. Note that the third dose of fulvestrant must be on Day 29, which should be equivalent to Cycle 2 Day 1.
- ^d LHRH analogue dosing and administration will be per institutional guidelines. Throughout the treatment period, LHRH analogue will be administered to/taken by premenopausal women and perimenopausal women per institutional guidelines
- ^e After screening, all subsequent radiographic scans for disease assessments may be done within a ±7-day time window and based on 8-week intervals timed from Cycle 1 Day 1. Initial responses should be confirmed, if feasible, with a repeat scan 4 weeks (+1-week window) following initial documentation of objective response. The schedule of response assessments should not be adjusted after the confirmatory scan and should maintain the schedule of every 8 weeks timed from Cycle 1 Day 1. Data on breast cancer serum tumor markers, if monitored, should also be collected at the time of disease assessment. Screening bone scintigraphy should be done at the same time as screening disease assessment. For subjects with new lesions identified by post-baseline bone scintigraphy, targeted assessment by Xray, CT scan with bone windows, or MRI will be performed to confirm findings. After screening, brain scans will be required per protocol only for subjects with findings on the screening brain scan; for subjects without findings on the screening brain scan, subsequent brain scans will be done per institutional standard of care.
- ^f May be done within 3 days before study drug administration; tests do not need to be repeated if done within the prior 3 days. Notes: Height will be measured only at screening. Weight will be measured as part of all physical examinations. Additional coagulation tests may be done per institutional standards for subjects taking fulvestrant.
- ^g Only if indicated.
- ^h See [Appendix B](#) for extensive sampling timepoints or [Appendix C](#) for sparse sampling timepoint. Note: Day 2 and Day 5 visits are **not** required for subjects on sparse sampling. The EOT PK sample is only required for subjects who have completed < 6 months of months of treatment.
- ⁱ See [Section 7.1](#) for details. Archived tumor tissue is allowed if new is unobtainable.
- ^j On applicable dosing days, the assessment should be performed predose.
- ^k On applicable dosing days, the assessment should be performed predose and postdose.
- ^l On applicable dosing days, the assessment should include one performed within 15 minutes of end of infusion.

- ^m On Cycle 1 Day 1 and Cycle 4 Day 1, a 12-lead ECG will be recorded predose and at 1 hour (± 15 minutes) after the end of the ZW25 infusion. On Day 1 of Cycle 3 and every 3 cycles thereafter (Cycle 3, 6, 9, etc.), a 12-lead ECG will only be recorded predose. ECGs will also be recorded at screening, EOT, and 30-day follow-up visit.
- ⁿ Only at disease progression and only at either EOT or follow-up, not both.
- ^o Cycle 4 and every even-numbered cycle thereafter.
- ^p Optional biopsy at disease progression if subject provides additional consent.
- ^q After screening, an echocardiogram/MUGA should be done at Cycle 3 Day 1 (± 7 -day time window; approximately 8 weeks after Cycle 1 Day 1), then all subsequent scans should be done every 12 weeks thereafter (Day 1 of Cycle 6, 9, 12, etc.) within a ± 7 -day time window. An echocardiogram/MUGA is not required at EOT if ≤ 3 months since the previous scan.
- ^r Should take place as soon as possible after a subject permanently stops all study treatment and definitely within 14 days after the last dose of study drug (ZW25, palbociclib, and/or fulvestrant).
- ^s The scans for these assessments do not have to be performed at EOT if ≤ 4 weeks since the previous scans. If the scans were not done at the EOT visit or within the 4 weeks prior to the safety follow-up visit, these assessments should be performed at the time of the safety follow-up visit.
- ^t AESIs should continue to be followed until resolution or return to baseline. Note: From the time of consent to immediately before the first dose of any study drug on Cycle 1 Day 1, only study protocol-related AEs should be recorded. A protocol-related AE is defined as an untoward medical event occurring as a result of a protocol mandated procedure.
- ^u Not required if ≤ 2 weeks since last sample.
- ^v Subjects who discontinue treatment for reasons other than progressive disease or start of subsequent anticancer therapy will continue in follow-up with disease assessments approximately every 8 weeks (± 7 days) after the previous scan until disease progression or start of subsequent anticancer therapy. If subjects enter this follow-up period before 24-weeks have elapsed since the start of study treatment, a disease assessment must be done at 24-weeks from the start of treatment (not required if ≤ 4 weeks since last disease assessment or if disease progression has already been documented). Responses that are initially observed during this follow-up period should be confirmed with disease assessment 4 weeks (+1 week) later. Following progression or start of subsequent anticancer therapy, disease assessments will be discontinued, and subjects will enter long-term follow-up for survival status. Data on survival will be collected via clinic visits (if feasible) or via telephone calls every 3 months (± 7 days) after the last follow-up visit. Subjects may be discontinued from the study due to death, lost to follow-up, consent withdrawal or study termination by sponsor.
- ^w Only if a subject had an ongoing anti-ZW25 ADA present at the safety follow-up visit. These will be discontinued after the resolution of ADA.
- ^x Via clinic visits (if feasible) or via telephone calls every 3 months after the last follow-up visit.
- ^y Plasma chemistry allowed if serum chemistry not available.
- ^z Per Memorandum MTF- 011 (dated 28 February 2023), PK and ADA sample collection should be stopped after completing Cycle 4, except for at the EOT visit and 2 additional collection time points for ADA at the Safety and Efficacy Follow-up visits.

